4 STUDY DESIGN

4.1 OVERALL DESIGN

This is a pilot randomized, controlled clinical trial to establish the intervention protocol's feasibility, acceptability, and fidelity, as well as preliminary effect size data. All study participants will undergo informed consent including authorization to view the child's medical record and consent to participate in action planning, health coaching, and weekly text message surveillance.

To participate in this study, a patient must be cared for at one of two sites (University of Wisconsin/American Family Children's Hospital or UCLA/Mattel Children's Hospital) in their complex care or cerebral palsy clinical programs, and meet study inclusion criteria, which include presence of severe cerebral palsy and respiratory care needs (see **Section 5, Study Population** for details).

Following an intervention adaptation phase consisting of formative data from focus groups with primary caregivers, clinical teams and a group of national experts, this phase will employ the evidence-based Replicating Effective Program's framework for intervention adaptation and the Patient-Centered Outcomes Research Institute's standards for improving research of complex health interventions. The previously efficacious PACT (Plans for Action and Care Transitions) intervention has been adapted to prevent severe respiratory illness in children with severe cerebral palsy, and to increased dose triggers from text messages indicating a family's low confidence for their child to avoid a hospitalization in real-time. In addition, the Core Functions (standard components required for integrity) and Forms (the tailored activities to carry out the Core Functions) have been delineated. The adapted intervention is called RE-PACT, or Respiratory Exacerbation Plans for Action and Care Transitions.

RE-PACT involves action planning and health coaching to prevent and manage respiratory illness, as well as weekly text messaging surveillance of caregiver confidence for their child to avoid a hospitalization. All intervention families will receive respiratory illness action plans at study entry. Action plan content will be consistent with standard clinical care guidelines and will not differ from the recommendations of the child's clinical care team. Health coaching focuses on managing medications, understanding and responding to red flags, keeping patient-centered records, maintaining timely follow-up with primary or specialty care. Coaches focus on skill transfer to parent caregivers, achieved through structured face-to-face or virtual telehealth coaching and phone follow-up over a 2-week period. Just-in-time action planning and coaching activities are triggered by caregiver text message responses indicating low confidence (rating ≤ 4 on 1-10 scale) to avoid a hospitalization. The usual care, active control group will continue to receive comprehensive care coordination and medical management.

Study participants will be randomly assigned to receive usual care through the complex care clinical program, or the study intervention, RE-PACT. Random allocation will be concealed to research staff conducting recruitment and will use a 1:1 allocation with random block sizes of 2 and 4. Block randomization will be achieved with a computer-generated random number list prepared by the study

biostatistician having no clinical involvement in the trial. Randomization will be stratified by site to account for site-specific study characteristics.

RE-PACT will be run through three successively larger 6-month trials (“waves”), allowing ongoing protocol refinement according to pre-specified definitions of success for measures of feasibility, acceptability and fidelity. Each wave has a specific protocol refinement focus: Wave 1 – onboarding/training, recruitment, data collection; Wave 2 – randomization and intervention activities; Wave 3 – rapid enrollment and conducting all protocol activities with high-fidelity.

RCT participants in both groups will undergo assessments of demographic, clinical and caregiving measures reported through questionnaire and medical record review at baseline at 6 months after enrollment. Feasibility, acceptability and fidelity data will be collected through parent-report, medical record review, and research team logs monthly during the intervention, and, for control group participants, at 6 months after enrollment.

Data about research participants (children and their families) will be collected by study research assistants through electronic self-administered questionnaires or structured interviews with parents either over the phone or in person, abstraction of child medical record data by the study RAs, and (for intervention group families) through phone interactions and direct observation with health coaches in RE-PACT. Content of these assessments include parent-report questions about child and parent health, parent perceptions of child health, family socio-demographic information, care utilization, and experiences of caregiving.

Analyses will assess feasibility, acceptability, fidelity and effect size estimates (by comparing numbers of respiratory exacerbations between intervention and usual care groups). We will use pre-specified definitions of success for each of our feasibility, acceptability and fidelity measures. We anticipate being underpowered to assess the efficacy of the intervention in this pilot study, but to inform a future large RCT we will test differences between intervention and active groups in the primary and secondary clinical outcomes. For each of these measures, we will compare differences between intervention and active control group outcomes at 6 months controlling for their baselines. While we anticipate that the intervention and control groups will be similar due to random assignment, we will adjust for any variables in our analysis that are not equal between the groups given the small sample size. In addition, we will analyze for any effect of primary home language on the study outcomes, as this may affect families’ ability to navigate systems of care in the U.S. To explore theoretical intervention mechanisms, we will also test the mediating effect of caregiver capability, opportunity, and motivation measures on the relationship between intervention and respiratory illness outcomes.

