Primary Study Endpoints - Feasibility, Acceptability, Fidelity: The specific measures and pre-specified definitions of success are listed in **Section 3**. These measures will be summarized between each of the three waves with protocol adjustments made for any measures below the definition of success.

Clinical Endpoints:

- Primary clinical outcome is severe respiratory illness, defined as respiratory diagnosis requiring hospitalization. Respiratory diagnosis includes discharge diagnosis of any of the following: asthma, pneumonia

(community or hospital acquired), bronchiolitis, influenza, upper or lower respiratory tract infection, tracheitis, aspiration pneumonia/pneumonitis, chronic lung disease, respiratory failure.¹²⁰ Field-testing assessment of this endpoint with trained research personnel at study sites demonstrated inter-rater reliability (Kappa) > 0.9.

- Secondary outcomes include: total hospital days during severe respiratory illness, numbers of systemic steroid courses, systemic antibiotic courses, respiratory ED visits, and death. Systemic corticosteroid course is defined by oral or parenteral corticosteroid prescribed for respiratory diagnosis, including hydrocortisone, prednisone, prednisolone, or methylprednisolone at least 1 mg/kg/day (or 30 mg/day) x minimum 3 days, or dexamethasone at least 0.15 mg/kg/day (or 10 mg/day) x 1 or more days. Physiologic or stress replacement doses in adrenal insufficiency are excluded. Systemic antibiotic course is defined by oral or parenteral antibiotics prescribed for respiratory diagnosis x minimum 3 days. The specific antibiotics are derived from IDSA pediatric pneumonia guidelines¹²¹ and published literature.¹²² Respiratory ED visits are any ED visits not resulting in admission and have a discharge respiratory diagnosis.

Additional Assessment Measures:

MEASURES	SOURCE	MEASURE DETAIL
Covariates		
Child and Caregiver Demographics	Survey	Child: age, gender, primary language, race/ethnicity, payer, family structure Caregiver: relationship, age, gender, language, race/ethnicity, education, health literacy, ¹¹⁴ income, rurality
Confounders		
Child Clinical Characteristics	Electronic health record	Organ systems affected by chronic conditions, subspecialists in past year, medical technologies used (e.g., tracheostomy, gastrostomy, etc.), duration of enrollment clinical program, numbers of ED visits and hospitalizations in past year, and respiratory treatments at time of enrollment (medications and devices)

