9.1 STATISTICAL HYPOTHESES

- Primary Feasibility, Acceptability, Fidelity Endpoint(s): RE-PACT's primary outcomes will be analyzed descriptively, and evaluate feasibility, acceptability, fidelity using multiple approaches. Each outcome will be

assessed against our pre-specified measures of success, e.g., achieving at least 80% enrollment. By conducting iterative refinements over three waves of implementation, we expect to achieve success in all measures. We will assess all participant feedback using both quantitative and qualitative data to determine what study design changes would enhance a large-scale RCT. We will use inductive content analysis of qualitative data.

- Secondary Efficacy Endpoint(s): **To inform a future large multisite RCT, we will test** differences between treatment (I or AC) groups in the primary and secondary respiratory illness outcomes. Our goal with these analyses is to estimate effect sizes for the differences between groups. The primary clinical outcome is severe respiratory illness rate, defined as the total number of severe respiratory illnesses divided by the person-months over the 6 months period. The severe respiratory illness rate will be analyzed with negative binomial (NB) regression models to account for overdispersion in the count data. In the primary analysis, univariate NB regression analysis will be conducted with study arm as a predictor variable. Study site will be a stratification factor to account for stratified randomization. The observed effect size of the analysis will be quantified in terms of relative risk (RR) and reported along with the corresponding 95% confidence interval. A generalized linear mixed effects model with a logit link function and subject specific random effects will evaluate **longitudinal changes** in the severe respiratory illnesses within and between study arms. An autoregressive (AR) correlation structure will account for within subject correlations. In this analysis, presence/absence of severe respiratory illness at the monthly assessments will be the dependent variable; study arm will be included as a predictor variable, and study site as a stratification variable to account for the stratified randomization. **To investigate theoretical mechanisms**, we will test the mediating effect of caregiver capability, opportunity, and motivation (COM-B)¹¹³ measures on the relationship between intervention and respiratory exacerbations.

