9.4.3 ANALYSIS OF THE SECONDARY ENDPOINT(S)

Clinical Outcomes. We will test differences between treatment (intervention or control) groups in the primary and secondary respiratory illness outcomes. Our goal with these analyses is to estimate effect sizes for the differences between groups which will allow precise sample size calculations for a future large-scale trial.

Primary clinical outcome is the severe respiratory illness rate, defined as the total number of severe respiratory illnesses divided by the person-months over the 6-month follow-up period. The severe respiratory illness rate will be analyzed using a negative binomial (NB) regression model to account for overdispersion in the count data. For the primary analysis, univariate NB regression analysis will be conducted with study arm as a predictor variable. Study site will be included as a stratification factor in the primary analysis to account for stratified randomization. The observed effect size of the analysis will be quantified in terms of relative risk (RR) and reported along with the corresponding 95% confidence interval.

As a secondary analysis, multivariate NB regression analysis will be performed to compare the severe respiratory illness rates between study arms. In this analysis, clinical and demographic characteristics will be included as covariates in an initial non-parsimonious model. The least absolute shrinkage and selection operator (lasso) and elastic net penalty methods for negative binomial regression models will be utilized to identify a parsimonious model with independent covariates. These methods are considered state-of-the art techniques for variable selection (Wang Z., et al. Stat Methods Med Res. 2016).

Longitudinal changes in the severe respiratory illnesses within and between study arms, will be evaluated with generalized linear mixed effects model with a logit link function and subject specific random effects. An autoregressive (AR) correlation structure will be utilized to account for within subject correlations. In this analysis, the presence/absence of severe respiratory illness at the monthly assessments will be the dependent variable, study arm will be included as a predictor variable and study site as a stratification variable to account for the stratified randomization.

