9.4.5 BASELINE DESCRIPTIVE STATISTICS

Study confounders and covariates (see **Section 8.1** for specific measures) will be summarized and compared at baseline. Given the small sample size, we will conduct adjusted and unadjusted analyses for variables that are statistically significantly different at baseline.

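### The sections disagree on whether the primary clinical rate ratio is baseline-adjusted, no single adjusted estimate is pre-specified, and the imbalance rules pick covariates by chance

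*Combined protocol and SAP*

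**What the plan says.** Section 4.1 first says that the arms will be tested on the primary and secondary clinical outcomes. It then states, for each of them, that "we will compare differences between intervention and active control group outcomes at 6 months controlling for their baselines". The next sentence adds that "we will adjust for any variables in our analysis that are not equal between the groups given the small sample size". The same rule recurs in 5.5 and 9.3. It has no threshold and names no model.

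Section 9.1 says: "In the primary analysis, univariate NB regression analysis will be conducted with study arm as a predictor variable". Section 9.4.3 repeats that "univariate NB regression analysis will be conducted with study arm as a predictor variable". Both add study site because randomization is stratified by site. Neither has a baseline term.

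Two further routes to adjustment follow:
- In 9.4.3, a model labelled secondary, in which "clinical and demographic characteristics will be included as covariates in an initial non-parsimonious model", reduced by lasso or elastic net.
- In 9.4.5, the statement that "we will conduct adjusted and unadjusted analyses for variables that are statistically significantly different at baseline".

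Section 8.1 lists, among the child's clinical characteristics, "numbers of ED visits and hospitalizations in past year" and respiratory treatments at enrollment. It lists no baseline count of respiratory events. Section 9.4.3 says the effect sizes are wanted for planning, "which will allow precise sample size calculations for a future large-scale trial".

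**The concern.** These statements cannot all govern one estimate. Section 4.1 requires a baseline term for the primary clinical outcome, and 9.1 and 9.4.3 leave it out. The conflict is not only between overview and detail: 9.3 sits in the statistical section and is also unconditional.

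Section 4.1 cannot be carried out literally either. The baseline of severe respiratory illness would be a prior respiratory hospitalization count, and 8.1 lists only hospitalizations and ED visits in general.

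The routes that do lead to an adjusted estimate choose covariates from the data, by penalized selection or by observed imbalance. Under valid randomization a baseline difference is chance, so an imbalance trigger carries no information about whether the variable predicts outcome. At stake are some precision and a single, foreseeable baseline-adjusted rate ratio to carry into the next trial.

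**Working it through.** The plan gives no figure for this point. The power range in 9.2 (19-88%) could not be reproduced with six months of exposure; that is a separate matter. Only the event rate, overdispersion and sample size are taken from 9.2.

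**1. How often the imbalance rules fire**

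Variables listed in 8.1 as covariates and confounders: child demographics 6, caregiver demographics 9, child clinical 7, caregiver strain and mental health 4 (three strain scores and the PHQ2). Total 26.
- Expected significant differences at 0.05: 26 × 0.05 = 1.3.
- At least one, if independent: 1 − 0.95^26 = 74%.
- At least one, with equally correlated test statistics: 72% (correlation 0.1), 68% (0.2), 62% (0.3), 48% (0.5).
- Past-year hospitalizations specifically: about 5%, however prognostic they are.
- Read literally, the unequal-variable rule covers nearly everything. With 45 v 45, a binary variable is exactly equal in only 8% of trials at 50% prevalence and 14% at 10%.

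**2. Precision at stake, closed form**

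Inputs: control mean 0.5 per 6 months (one per year, 9.2); φ = 1.0 (9.2); rate ratio 0.6, so intervention mean 0.3 (the 40% reduction in the earlier trial, 2.2); 45 × 0.9 = 40.5 analysed per arm.

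Unadjusted: var(log RR) = (1/0.5 + 1/0.3 + 2 × 1.0)/40.5 = 7.33/40.5 = 0.181, SE 0.426. The 95% CI runs 2.30-fold each way.

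Now assume a binary predictor present in half the children. Relative means are 0.5 and 1.5 (3-fold) or 0.182 and 1.818 (10-fold), with variance 0.25 or 0.669. Residual φ = 2/(1 + variance) − 1 = 0.60 or 0.198. Information per child is the average of m/(1 + φm) over the two groups, where m is the group mean and φ the residual value.
- 3-fold: 0.367 control, 0.246 intervention; variance (1/0.367 + 1/0.246)/40.5 = 0.168. Gain 0.181/0.168 = 8%; CI 2.23-fold.
- 10-fold: 0.430 and 0.273; variance (1/0.430 + 1/0.273)/40.5 = 0.148. Gain 22%; CI 2.12-fold.

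The 10-fold case is an upper bound. The figure in 2.2 concerns respiratory illness in the past year, which 8.1 does not list.

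**3. Precision at stake, simulation with the all-cause count**

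3,000 trials per scenario, 40 analysed per arm, gamma frailty with φ = 1, respiratory mean 1 per year, NB maximum likelihood with site in both models. The covariate is log(past-year count + 1). Non-respiratory admissions are assumed at 1 or 3 per year; 3 follows from the 25% respiratory share in 2.2 with one respiratory admission per year. The trigger is a t-test on the covariate at p < 0.05.

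| Other admissions | Variance ratio, unadjusted/adjusted (95% interval) | Ratio if adjusted only when triggered |
|---|---|---|
| Risk fully shared, 3 per year | 1.22 (1.18-1.27) | 1.055 |
| Risk fully shared, 1 per year | 1.13 (1.09-1.17) | 1.035 |
| Independent, 3 per year | 1.03 (1.01-1.04) | 1.006 |
| Independent, 1 per year | 1.04 (1.02-1.06) | 1.009 |
| Shared, risk redrawn for half the children | 1.03 (1.01-1.05) | 1.019 |
| Independent, redrawn for half | 0.99 (0.98-1.01) | 1.002 |

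Smaller repeat runs (900-1,000 trials) gave gains of 17-20% with fully shared risk, about 10% with risk redrawn for a quarter of the children, and -1% to 3% in the weak scenarios.

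Power was 22-24% unadjusted and 22-26% adjusted, a change of -0.1 to +3.2 points. Wald type I error was 5.0-6.0% unadjusted and 4.2-6.0% adjusted. The two rate ratios from one trial differed by a median of 1.02- to 1.14-fold (90th percentile 1.11- to 1.43-fold). A separate run with lognormal frailty gave a 90th percentile of at most 1.21-fold. That spread is the same precision loss seen another way, not a further harm.

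**The case against.** The strongest reply is that the primary estimate is already identified. Sections 9.1 and 9.4.3 name the same model, 9.4.3 labels the covariate model secondary, and 4.1 is a design overview. Section 9.4.5 reports adjusted results beside unadjusted ones, so a trigger that fires does not displace the primary rate ratio. This stands. A reader might infer that the plan has no primary estimate, or a biased one; the documents do not support that.

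It is also fair that the gain is small in most scenarios, and that the larger gains need non-respiratory admissions to share the child's respiratory risk fully and stably, which no section supports. A reader might infer a gain of 22% or more from the 10-fold figure in 2.2; that figure belongs to a predictor that 8.1 does not list. The all-cause count is only a proxy for the outcome's own baseline. The 74% is a ceiling, because several of the 26 variables overlap. Nor should 8.1 be read as having no respiratory baseline information, since it lists respiratory treatments at enrollment.

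Finally, the clinical outcome is a secondary endpoint in a pilot that accepts low power, and 9.4.1 refers to a separate detailed SAP that may settle the model. It is not among these documents, and the protocol sections would still conflict. What survives is the contradiction, the chance-driven covariate rules, and the lack of one pre-specified adjusted estimate.

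**Conclusion.** The concern holds as an inconsistency with a modest statistical cost. Sections 4.1 and 9.3 cannot be reconciled with the arm-plus-site model in 9.1 and 9.4.3. The imbalance rules select covariates by chance. No single baseline-adjusted rate ratio is fixed in advance.

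The arm-plus-site estimate and its interval remain valid. The effective-sample gain from pre-specified adjustment is about -1% to 4% if past-year admissions share little risk with respiratory admissions or risk changes over time, and about 13-22% only if risk is fully shared and stable. Adjusting only when the significance trigger fires captures 0-6%. Power changes by about 0-3 points. These sizes rest on the event rate and overdispersion in 9.2, an assumed rate ratio of 0.6, and an assumed rate of other admissions. The change should be made, mainly because it is nearly free and the estimate is a stated input to the next trial.

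**What to change.** 1. Delete the unequal-variable rule in 4.1, 5.5 and 9.3 and the significance-triggered rule in 9.4.5. Keep the baseline table descriptive.
2. Pre-specify one baseline-adjusted NB model: arm, site and log(past-year hospitalization count + 1), with log person-months as offset. State a rule for children under 12 months, who lack a full past year. Make 4.1 describe this model, and claim baseline control only for outcomes whose model contains such a term. Preferably this is the primary model, with arm plus site as the sensitivity analysis. If the sponsor keeps arm plus site as primary, this becomes the single named adjusted analysis.
3. Keep the lasso/elastic-net model secondary, with arm and site unpenalized.

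The cost is protocol and SAP wording; the count is already collected, and 9.4.1 leaves the SAP open until database lock. The downside is one extra parameter, with little or no gain if past-year admissions predict poorly (-1% in the worst scenario simulated).

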4.2 SCIENTIFIC RATIONALE FOR STUDY DESIGN

Rational for the study design. Conducting this pilot study will provide a high degree of certainty that the final RE-PACT protocol is feasible, acceptable and can be delivered with fidelity. This is a critical approach to designing interventions that can be integrated in diverse, real-world, settings and sustained.

Using an RCT design (i.e., with a control group who do not receive intervention) is necessary to establish effect sizes needed to adequately power an efficacy trial. The findings from this study will allow precise estimation of effect sizes to conduct a fully powered, multisite hybrid Type 2 effectiveness-implementation RCT.

Rationale for the type and selection of control conditions. The control group will be randomly assigned, allowing the study team to conclude that endpoint differences between each group are most likely due to the intervention itself.

Potential problems associated with the control group. The control group may have pre-existing respiratory action plans created during routine clinical care. In addition, the coach may have difficulty avoiding contaminating the control group by inadvertently conducting coaching activities to those not assigned to the intervention group. This risk will be minimized since action plans using the study protocol will only happen for intervention subjects, and coaching is triggered only through mHealth text responses and texting will only be set up for those assigned to the intervention.

